3.2 STUDY ENDPOINTS

3.2.1 PRIMARY ENDPOINT:

[Length of time \(hrs/days\) to gastrointestinal tract recovery](#)

3.2.1.1 PRIMARY ENDPOINT DEFINITION:

Time to gastrointestinal recovery will be measured by the following: Time to first flatus, time to toleration of a liquid diet, time to toleration of a solid diet, time to toleration or oral pain medications, time to first bowel movement, time to GI-2 recovery, time to GI-3 recovery, incidence of nasogastric tube insertion, episodes of emesis, use of anti-nausea medication, nausea, bloating, incidence of diet reduction or restriction, and initiation of TPN.

Time to first flatus and time to first bowel movement are patient reported endpoints that occur during the hospitalization. Patients will be asked about flatus twice daily by the physician or a qualified study or clinical staff member. Additionally, patients will be instructed to notify the nurse following first flatus and/or bowel movement so that the time can be recorded.

Toleration of a diet and toleration of oral pain medication are defined as ingestion of diet or medications that occurs without vomiting or significant nausea for four hours following ingestion.

GI-2 recovery is defined as both toleration of solid food and occurrence of first bowel movement. GI-3 recovery is defined as toleration of solid food and either occurrence of first flatus or occurrence of first bowel movement.

Patients requiring nasogastric tube insertion, requiring reduction or restriction of diet, having episodes of emesis, and/or needing initiation of TPN will be recorded. VAS

nausea, bloating and pain scores will be recorded by nursing staff at least twice each day. The number of doses of anti-nausea medication administered during the hospitalization will also be recorded.

3.2.2 *SECONDARY ENDPOINT(S):*

[Length of hospital stay](#), 30-day treatment related morbidity and re-admission rates, and post-operative pain scores.

3.2.2.1 *SECONDARY ENDPOINT DEFINITION(S):*

Length of stay will be measured in hours from the time that surgery is completed until the hospital discharge order is written (hrs/days).

Treatment related morbidity and re-admission rates will be assessed from the time surgery is completed to 30-days post-operatively. Treatment related morbidity and re-admission rates include: POI, indigestion, and any event determined by the attending physician to be directly related to treatment.

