5.4 ADVERSE EVENT REPORTING

If your study collects patient specific safety data, provide timelines and a detailed description of procedures for collecting, assessing and reporting adverse events. A technical guide is available upon request to assist you in completing the following section.

It is the responsibility of the investigator(s) to oversee the safety of the study. The safety monitoring will include careful assessment and appropriate reporting of complications/events as noted below.

Adverse events will be reviewed for clinical relevance and cause relation and reported as the events occur.

The ACS NSQIP Variables and Definitions guidance document will be used to ensure consistency of defining and reporting the complications or events in this study.

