5.4.3 EXPECTEDNESS OF AE

An AE is considered *unexpected* if the specificity or severity is not consistent with the applicable product information. In this case, where a study is being performed prospectively outside of the current labeled use (e.g., the investigator holds their own IND), the Investigator Brochure is considered the applicable product information.

Warnings and precautions as provided in the prescribing information packet include:

1. A higher number of myocardial infarctions was reported in patients treated with alvimopan 0.5 mg twice daily compared with placebo 12 in a 12-month study in patients treated with opioids for chronic pain, although a causal relationship has not been established

2. Patients recently exposed to opioids are expected to be more sensitive to the effects of ENTEREG and therefore may experience abdominal pain, nausea and vomiting, and diarrhea.
3. Not recommended in patients with severe hepatic impairment.
4. Not recommended in patients with end stage renal disease.
5. Most common adverse reaction (incidence >1.5%) occurring with a higher frequency than placebo among ENTEREG-treated patients undergoing surgeries that included a bowel resection was dyspepsia.
6. Not recommended in patients with complete GI obstruction or in patients who have surgery for correction of complete bowel obstruction.
7. Not recommended in pancreatic or gastric anastomosis.

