5.4.4 RECORDING AND REPORTING AN AE

If AEs are collected, any AE, regardless of seriousness, severity, or causal relationship to a drug, should be recorded on the case report form or SAE form. For retrospective studies, investigators should report all AEs identified during the study period defined in the protocol.

Any AE, regardless of seriousness, severity, or causal relationship to the study medication, will be recorded on the case report form or SAE form. The form contains fields that allow for complete evaluation of an AE. All AEs starting with the first intervention or dose of study medication and throughout the duration of the study (through last patient visit) will be monitored.

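### The only 30-day morbidity and readmission endpoint counts events other than ileus and indigestion only if the attending physician attributes them to treatment, and no all-cause comparison by arm is planned.

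*Combined protocol and SAP*

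**What the plan says.** Section 3.2.2 lists, after length of stay, "30-day treatment related morbidity and re-admission rates, and post-operative pain scores" as secondary endpoints. Section 3.2.2.1 sets the window, "Treatment related morbidity and re-admission rates will be assessed from the time surgery is completed to 30-days post-operatively", and gives the content in one sentence that serves both rates. It names postoperative ileus and indigestion, and then "any event determined by the attending physician to be directly related to treatment".

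Other sections bear on this:

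- Section 3.1.1 puts safety next to efficacy in the primary objective. Section 3.1.2 words the secondary objective as treatment-related morbidity.
- Section 5.4.4 makes recording independent of cause: "Any AE, regardless of seriousness, severity, or causal relationship to the study medication, will be recorded on the case report form or SAE form". Section 5.4.5.2 repeats the rule. Recording runs from the first intervention or dose to the last visit.
- Section 5.4 adopts a standard set of complication definitions: "The ACS NSQIP Variables and Definitions guidance document will be used". Section 3.2.2.1 does not refer to it.
- Section 5.4.2, in the text available, defines three causality categories: not, unlikely and possibly related.
- Section 4.4.3 keeps the investigator and study staff blinded.
- Section 6.3 names two outcomes for comparison between the groups, time to bowel function recovery and length of stay, both by t-test.

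**The concern.** The study hypothesis (section 2) includes a shorter hospital stay. Section 5.3 allows discharge before solid food is tolerated and before a bowel movement, and section 1 describes ileus as a frequent cause of readmission. Total readmissions are the natural counterweight to a shorter stay. A rate that leaves out readmissions nobody attributed to treatment cannot serve that purpose.

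The filter is also poorly defined. Directly related is not a category in section 5.4.2, so the endpoint cannot be derived from the causality field by a fixed rule. Treatment is not tied to the study drug either. It could cover the repair or the postoperative care, which section 5.3 calls a treatment pathway. Two physicians could classify the same event differently, each with support in the text.

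A physician blinded to assignment judges cause without knowing whether the patient took alvimopan. Comparing all events between randomised arms needs no such judgement. Myocardial infarction illustrates the difficulty. Section 5.4.3 reports that "A higher number of myocardial infarctions was reported in patients treated with alvimopan", in a 12-month study at a different dose in patients taking opioids for chronic pain, and adds that causality has not been established. A physician who follows that text could reasonably decline to call an infarction directly related, and it would then fall outside the endpoint.

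**Working it through.** The plan gives no event rate, margin or power for this endpoint, so there is no stated figure to reproduce. The check compares the sections and then uses assumed rates to see what can be said about size.

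**1. What is recorded against what is counted**

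| | Adverse event record (5.4.4, 5.4.5.2) | Endpoint (3.2.2.1) |
|---|---|---|
| Cause | Any | Ileus and indigestion; otherwise only if judged directly related |
| Start | First intervention or dose | End of surgery |
| End | Last patient visit | 30 days |
| Definitions | ACS NSQIP | None cited |
| Planned comparison by arm (6.3) | None named | None named |

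The recorded set is wider than the counted set, and no planned comparison uses the difference.

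**2. How many readmissions could be left out (assumed)**

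Assume 10% are readmitted for any cause: 0.10 × 70 = 7 per arm. Let k be those due to ileus or indigestion, which count without attribution, and let a be the share of the others that is attributed.

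Counted = k + a(7 − k). Left out = (1 − a)(7 − k).

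With a between 0.3 and 0.7 (assumed):

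- k = 0: counted 2.1 to 4.9, left out 4.9 to 2.1.
- k = 3: counted 3 + 0.3 × 4 = 4.2 to 3 + 0.7 × 4 = 5.8, left out 2.8 to 1.2.
- k = 6: counted 6.3 to 6.7, left out 0.7 to 0.3.

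The loss runs from most of the readmissions to almost none, depending on k, which the documents do not give.

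**3. Effect on power (assumed)**

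Take true all-cause rates of 15% and 5%, n = 70 per arm, two-sided 5%. The result is the same whichever arm has the higher rate.

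Power = Φ[(d − 1.96·se0)/se1], where d is the difference, se0 = √(2p̄(1 − p̄)/n) with p̄ the mean of the two rates, and se1 = √{[p1(1 − p1) + p2(1 − p2)]/n}.

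- All events counted, 15% v 5%: d = 0.10, se0 = 0.0507, se1 = 0.0500. Power = Φ(0.01) = 50.5%.
- Half of events attributed in each arm, 7.5% v 2.5%: d = 0.05, se0 = 0.0368, se1 = 0.0366. Power = Φ(−0.61) = 27.2%.
- Attribution removes only background events, 2.5 points from each arm, 12.5% v 2.5%: d = 0.10, se0 = 0.0445, se1 = 0.0437. Power = Φ(0.29) = 61.5%.

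An attribution filter unrelated to true cause lowers power. An accurate one raises it. The documents do not say which applies.

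**The case against.** The strongest reply is that nothing is lost. Every adverse event goes on a form whatever its cause, so an infarction is recorded whether or not anyone attributes it. This stands as far as it goes. A reader might infer that the trial fails to capture these harms, and the documents do not support that: the events are missing from the endpoint, not from the safety record. But section 6.3 plans no comparison of that record by arm, so recording alone does not fill the gap.

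Second, the endpoint matches the secondary objective, which is itself worded as treatment-related. That is true, and it is why the attributed rate should stay as a supportive summary. It does not meet the safety part of the primary objective.

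Third, the word include may be open-ended, and treatment may cover surgery. Both readings are possible. However, the list closes with a general clause that is itself limited to attributed events, so the natural reading keeps the filter. A wider meaning of treatment would admit more events but would still leave the decision to the attending physician's opinion.

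Three further inferences are tempting and unsupported:

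- That a fixed share of the readmission information, such as 30% to 70%, is lost. That range applies the filter to all readmissions, although ileus and indigestion count without it.
- That power to see harm necessarily falls. The third case above shows it can rise.
- That the filter favours one arm. Blinded attribution makes that less likely, and the documents give no evidence of it.

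**Conclusion.** The concern holds as a matter of endpoint definition. The trial's only 30-day morbidity and readmission endpoint leaves out unattributed events other than ileus and indigestion, uses a causality term the protocol does not define, and is not backed by any planned all-cause comparison. As written, it cannot show whether a shorter stay comes with more readmissions overall.

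The size is not known. In the illustrations, 0.3 to 4.9 of 7 readmissions per arm are left out, and power moves from 50.5% down to 27.2% or up to 61.5%. All of this rests on assumed rates and assumed attribution behaviour. Even with every event counted, the trial has limited power for an outcome of this kind, so the gain is chiefly a rate that can be interpreted.

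That an all-cause readmission count can already be drawn from the trial's data is an inference. The event behind a readmission should be recorded as an adverse event, but no section in the available text names a readmission field, and the data collection schedule (Appendix I) is not part of that text. The primary analysis and the sample size are unaffected.

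**What to change.** In section 3.2.2.1, define two 30-day secondary endpoints: all-cause readmission and all-cause morbidity, the latter by the ACS NSQIP definitions already adopted in section 5.4. In section 6.3, state that both are compared by assigned arm. Keep the treatment-related subset as a supportive summary, say whether treatment means the study drug or also the surgical care, and tie the term to a category in section 5.4.2.

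Confirm that the case report form captures every readmission within 30 days whatever its reason, or add that field.

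The cost is revised wording, one more table and at most one form field. The downside is that events unrelated to the drug will add some noise to the comparison.

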1 STUDY RATIONALE/BACKGROUND

Alvimopan (Entereg) is an orally administered peripherally acting μ -opioid receptor antagonist that has been shown to decrease the duration of postoperative ileus.^{2,5,8,9} Multiple double-blinded, randomized, placebo-controlled trials, have shown Alvimopan to reduce both the time to gastrointestinal recovery and the time to hospital discharge following bowel resection. This benefit was achieved without compromising pain management.¹⁰ Alvimopan selectively and competitively inhibits the μ -opioid receptors in the GI tract, but is unable to cross the blood-brain barrier. This prevents Alvimopan from affecting the central nervous system pathway that controls analgesia, allowing it to decrease postoperative ileus time without compromising pain control.¹⁰ In addition to accelerated gastrointestinal recovery and reduced length of hospital stay, the use of Alvimopan also significantly decreased the number of adverse events (most notably nausea and vomiting), and decreased the need for postoperative nasogastric tube reinsertion. These improved clinical outcomes had further impact by leading to lower hospital costs and increased patient satisfaction.^{3,5,8,9} Alvimopan is FDA approved for patient use with the intent of accelerating upper and lower gastrointestinal recovery following bowel resections. To date, no studies have been conducted regarding the use of Alvimopan in patients undergoing ventral hernia repairs.

Conservative estimates suggest that the incidence of ventral incisional hernia after abdominal surgery via midline laparotomy is 10-20%.^{1,4,7} The occurrence of a ventral incisional hernia is associated with significant patient discomfort, disability and subsequent morbidity. These factors lead most patients suffering from a ventral incisional hernia to pursue elective repair. In 2005, there were greater than 348,000 ventral hernia repairs in the United States alone.¹⁴ If left unrepaired, these hernias can

increase in size causing pain, abdominal wall deformity, skin breakdown, intestinal obstruction and/or intestinal strangulation.⁴

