Post-operative pain scores will be obtained from patients daily until hospital discharge, 2-weeks post-operatively, and 30-days post-operatively using the Visual Analog Pain Scale (scale, 1-10) and the Hernia-Related Quality-of-Life Survey (HerQLes).

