4.3.3 SAMPLE SIZE DETERMINATION

A total of 140 patients are expected to undergo research related treatments. The study will contain one open surgery arm. The open surgery arm will be a single-site prospective, randomized, double-blinded, placebo-controlled clinical trial with 1:1

randomization between the study drug and placebo with 70 patients in each group for a total of 140 patients in the study. An interim evaluation of efficacy will be conducted separately in the open surgery arm when half the patients have been recruited.

This study is expected to enroll up to 140 subjects from one academic medical center (Froedtert Hospital and the Medical College of Wisconsin) a site that performs state of the art hernia repairs and is a high volume hernia practices.

The study has been designed to provide at least 80% power to detect a 24-hour decrease in the time to return of bowel function in the treatment group compared to the control group at a one-sided 2.5% significance level. This corresponds to a two-sided 5% significance level, but acknowledges the one-sided nature of the study hypothesis. Based on data from studies of the experimental treatment in other contexts, as well as internal data, we expect a standard deviation of 48 hours. Adjusting for the increase in sample size to accommodate the planned interim analysis, 64 evaluable patients per group will provide the desired power. More details of the power characteristics are shown under the Interim Analysis section. We will recruit 70 patients in each arm to accommodate a 5-10% dropout rate.

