4.4.3 BLINDING

The study will be performed in a double-blind fashion. The investigator, study staff, subjects, and monitors, will remain blinded to the treatment assignment. Alvimopan and the placebo will be visually identical and will be similarly packaged and administered.

The identity of the study drug may only be revealed if the subject experiences a medical emergency whose management would require knowledge of the blinded treatment assignment. The master randomization code list will be maintained by the IDS. Prior to unblinding, the surgeon or other care provider must contact the study principle investigator, and every attempt must be made by the treating surgeon to discuss the intended unblinding with the principle investigator (or a designee from IDS). All cases of unblinding, including justification for unblinding, must be fully documented by the principle investigator, site investigator, and IDS designee. The principle investigator may obtain the identity of the study drug dispensed to a subject through IDS.

If the subject becomes unblinded, the subject will continue to be followed for adverse events up to 30 days, or 14 days past discharge if the patient is an inpatient after 30 days, but the efficacy data from this point will be carried forward and analyzed in the intent-to-treat analysis.

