6 DATA COLLECTION AND ANALYSIS

6.1 DATA COLLECTION

For each subject who meets inclusion criteria, a clinical report form (CRF) must be completed and signed by the investigator to certify that the data within each CRF are complete and correct according to data collection schedule (Appendix I). Every effort

should be made to respond to all questions on each CRF page, completion of the data is required by the protocol. The header section of each CRF page should be completed to identify the Investigators/surgeon and subject identification.

Upon receipt of completed CRFs and prior to entering data into the aggregate data summary table, the site-coordinator will ensure the accuracy of data recorded by comparison to supporting source documents. Adherence to proper recording of information as well as assuring that corrections are being made will also be addressed.

One interim analysis will be conducted when the first half of patients in each group (35 treatment and 35 control) complete their 30-day follow-up visit. Specifically, the interim analysis will be blinded and conducted at a nominal 0.0031 one-sided level of significance, while the final analysis will be conducted at a nominal 0.0219 one-sided level of significance. These values were calculated using a third-degree Kim-DeMets power alpha-spending function evaluated at the halfway point. If the actual information fraction at the time of the analysis is different, or the DSMC requests additional unblinded analysis, the significance levels will be adjusted using the alpha-spending function.

Results of the interim analysis will determine if it is futile to continue patient enrollment based on statistically significant differences (24 hour decrease in the time to return of bowel function in the treatment group compared to controls at a one-sided 2.5% significance level between the treatment and control groups). In addition, the MCW IRB in collaboration with the study investigators may terminate the study at any time to maintain patient safety.

The following table shows the probability of early stopping and the overall power of the study for various hypothetical effect sizes. If the design assumptions are correct, the study will stop early for efficacy with 23% probability, but if the actual effect is 50% larger (due to larger mean difference or smaller within-group standard deviation), then the trial will stop early 60% of the time.

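### The supplied text plans no pre-operative pain VAS or HerQLes and no baseline-adjusted comparison, so the 2-week and 30-day scores lose precision that a cheap measurement would give.

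*Combined protocol and SAP*

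**What the plan says.** Section 3.2.2 lists among the secondary endpoints "30-day treatment related morbidity and re-admission rates, and post-operative pain scores". Section 3.2.2.1 gives the times: "Post-operative pain scores will be obtained from patients daily until hospital discharge, 2-weeks post-operatively, and 30-days post-operatively using the Visual Analog Pain Scale", with the second instrument joined in the same sentence: "and the Hernia-Related Quality-of-Life Survey (HerQLes". Section 3.2.1.1 adds inpatient scoring: "nausea, bloating and pain scores will be recorded by nursing staff at least twice each day". None of these times precedes surgery.

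Section 1 describes the condition being operated on: "The occurrence of a ventral incisional hernia is associated with significant patient discomfort, disability and subsequent morbidity".

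Section 6.3 names a t-test for bowel recovery time and for length of stay, under intention to treat. It names no method for pain or HerQLes.

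Section 6.1 requires case report forms to be "complete and correct according to data collection schedule (Appendix I"). That appendix is not in the supplied text.

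Two design features bear on how much this matters. Section 4.3.3 specifies 1:1 "randomization between the study drug and placebo with 70 patients in each group", and section 4.4.3 says "The study will be performed in a double-blind fashion".

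**The concern.** The protocol says these patients have pain and disability from the hernia before the operation, and it uses a hernia-specific quality-of-life survey. Yet no supplied section plans to measure either before surgery. If that is the real schedule, three things follow.

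- **Precision.** Differences between patients in pre-operative status stay in the 2-week and 30-day scores as unexplained variation, and the interval for the arm difference is wider than it need be. Section 1 stresses that the drug should not compromise pain control, so a tight interval for pain has some value.
- **Interpretation.** Change within a patient cannot be reported. An absolute 30-day HerQLes score mixes earlier hernia burden with recovery from surgery.
- **Checking comparability.** Dosing starts before surgery (section 5.1), but eligibility is settled during it (section 4.4.1), and patients who need a nasogastric tube are excluded afterwards (sections 4.2.2 and 5.3). With no baseline score, nobody can see whether the patients who remain are still alike on pain and quality of life.

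An analysis method can still be written before unblinding. A pre-operative score cannot be collected once the operation is done.

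**Working it through.** **Inputs.** From the documents: 1:1 randomisation, 70 recruited and 64 evaluable per arm, a 24-hour difference, SD 48 hours, one-sided 2.5%, one interim look at half information. Not in the documents: the SD of the VAS or HerQLes, and the correlation r between a pre-operative score and the 2-week or 30-day score. I assume r = 0.3, 0.5 and 0.6 and work in units of the between-patient SD.

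**1. The plan's own figure.** It concerns the primary endpoint only. The fixed-design number is 2 × (1.960 + 0.842)² × (48/24)² = 62.8, so 63 per arm. With 64 per arm and a cubic spending function (0.025 × 0.5³ = 0.003125 at the interim), power is 23.14% + 57.21% = 80.35%. The plan states 22.9%, 57.1% and 80.0%. The sample size reproduces, and no pain or HerQLes quantity enters it.

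**2. Is the comparison of post-operative scores valid without a baseline?** In 20,000 simulated trials with 64 per arm and no treatment effect, the mean arm difference was 0.0004 SD (r = 0.3) and −0.0006 SD (r = 0.6). Two-sided type I error was 4.9% and 5.0%. It is valid under randomisation.

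**3. What adjustment gains.** ANCOVA multiplies the variance of the arm difference by 1 − r². The equivalent sample inflation is 1/(1 − r²). The detectable difference at 64 per arm (two-sided 5%, 80% power) is (1.960 + 0.842) × √(2/64) × √(1 − r²), which is 0.495 SD with no baseline.

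| r (assumed) | 1 − r² | Variance cut | 1/(1 − r²) | Detectable difference | Power where unadjusted power is 80% |
|---|---|---|---|---|---|
| 0.3 | 0.91 | 9% | 1.10 | 0.472 SD | 83.6% |
| 0.5 | 0.75 | 25% | 1.33 | 0.429 SD | 89.9% |
| 0.6 | 0.64 | 36% | 1.56 | 0.396 SD | 93.8% |

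**4. Why ANCOVA and not change scores.** With equal variances before and after, a change score has variance factor 2(1 − r): 1.4, 1.0 and 0.8. At r = 0.3 it is worse than ignoring the baseline. ANCOVA is better at all three values.

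**5. Chance imbalance.** The baseline difference between arms has standard error √(2/70) = 0.169 SD, or √(2/64) = 0.177 SD among evaluable patients. Its effect on the outcome is r times that: at 70 per arm, 0.05, 0.08 and 0.10 SD. This is already inside the unadjusted standard error, because r² × 2/n + (1 − r²) × 2/n = 2/n. Adjustment removes the first term, so this is the gain in step 3 seen another way and must not be added to it.

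**The case against.** The strongest objection is that the schedule itself is out of sight. Section 3.2.2.1 defines post-operative scores, so it would name post-operative times in any case. A baseline form would normally appear in Appendix I. This stands: one can say that the supplied text mentions no baseline, but not that the trial takes none.

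The second objection concerns the harm. A reader might infer that the 2-week and 30-day comparison is confounded by earlier hernia pain. The documents do not support that. The question is alvimopan against placebo, not the benefit of repair; allocation is randomised and blinded; and the endpoint is the post-operative score, not change. Step 2 bears this out. Nor should 0.17 SD of chance imbalance be read as extra error.

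Third, every r is assumed, and the values apply to the 2-week and 30-day scores. Daily inpatient pain after open surgery may correlate less with a baseline. The documents do not say how widely pre-operative pain varies, and the exclusion of patients with recent sustained opioid use may narrow it. These scores appear in neither stated objective and did not size the trial. All of this stands and limits the importance of the point.

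Fourth, a reader might see a contradiction between daily and twice-daily inpatient pain scores, or a burden from daily HerQLes. Twice-daily nursing scores satisfy a daily requirement, and a daily HerQLes is only one reading of a compressed sentence. Neither carries the point.

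One thing is left over. The reassurance in step 2 applies to the groups as randomised. Nasogastric-tube insertion is a listed component of the primary endpoint, so that exclusion could depend on treatment. A baseline would not repair such a loss, but it would help to check for it.

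**Conclusion.** The point holds as a cheap improvement, not as a flaw that invalidates a result. On the supplied text, the VAS and HerQLes are scheduled only after surgery and no baseline-adjusted analysis is planned. The randomised comparison of these scores remains unbiased in expectation. The cost is a variance that adjustment would cut by 9%, 25% or 36% at r = 0.3, 0.5 or 0.6, together with no within-patient change and no check of balance after exclusions. The size rests entirely on the assumed r, and the finding is conditional on Appendix I listing no baseline. The primary endpoint, its power and the planned 140 patients are unaffected.

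**What to change.** 1. Check Appendix I. If it already lists a pre-operative VAS and HerQLes, state this in section 3.2.2.1. If not, add one of each, taken after consent and before the pre-operative dose.
2. In section 6.3, specify that the 2-week and 30-day VAS and HerQLes scores are compared between arms by ANCOVA, with the pre-operative value of the same instrument as covariate.
3. Tabulate the baseline scores by arm for all randomised patients and for those remaining after the intra-operative and nasogastric-tube exclusions.

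Cost: one short questionnaire and one VAS per patient at a contact that already takes place, one case report form page, and a few lines of protocol text. No change to the sample size is needed. It helps only patients not yet operated on, so it should be settled before enrolment.
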